1. RSS ≥ 2.4
2. $\text{PCO}_2 > 65 \text{ mmHg}$ and/or $\text{pH} < 7.20$
3. nCPAP $> 8 \text{ cm}$
4. Three severe apneas with bradycardia within six hours requiring escalation of support

Infants were followed for their need for AeroFact and/or bolus dosing of surfactant. Tolerance of AeroFact dosing had the following data collected: changes in respiratory support over the first 28 days of life, BPD status at 36 weeks PMA and co-morbidities of prematurity/AEs monitored until the time of discharge.

2.2.2.1 APC-AF-CLN-001 Part I

Part I of the study was designed to determine the safety and tolerability of administering a single nominal dose of 216 mg/kg of aerosolized AeroFact (SF-RI 1) by nCPAP. Ten preterm infants who required nCPAP (machine CPAP) and satisfied the inclusion and exclusion criteria were enrolled into this part of the study.

After successful completion of Part I and a proceed recommendation by an Independent Data Safety Monitoring Board (DSMB), sites were permitted to begin enrollment into Part II of the study.

2.2.2.2 APC-AF-CLN-001 Part II

Part II of the study was designed to determine the safety and tolerability of administering up to four doses of aerosolized AeroFact (SF-RI 1) by nCPAP. Twenty (21) preterm infants were enrolled into this part of the study.

An initial nominal dose of 216 mg/kg of aerosolized SF-RI 1 was administered. Oxygenation and ventilation parameters were monitored as outlined in the protocol. Infants continued on nCPAP. Re-dosing of AeroFact (nominal dose of 216 mg/kg) occurred if the RSS to maintain SpO_2 between 90% and 95% (as measured by pulse oximetry) ≥ 2.0 and at least (1) 2 hours elapsed since the end of the first dose and (2) 4 hours elapsed since the end of either the second or third dose. Up to 3 additional doses of AeroFact within 96 hours were allowed.

2.2.3 Summary of Clinical Results

2.2.3.1 APC-AF-CLN-001-Safety Analysis Conclusions:

- The overall incidence of TEAEs was low among AeroFact patients; 3 patients (30%) had 1 or more TEAE(s) in Part I, and 5 patients (23.8%) had 1 or more TEAE(s) in Part II.
- There were no TEAEs which were assessed by the Investigator as related to the study drug, device, or procedure, and none led to premature discontinuation from the study drug or premature discontinuation from the study.
- The most common TEAEs reported were patent ductus arteriosus occurring for 1 patient (10%) in Part 1 and for 3 patients (9.5%) in Part II, and pneumothorax occurring for 1 patient (10%) in Part 1 and 1 patient (4.8%) in Part II.
- All TEAEs in Part I were mild and the majority of TEAEs in Part II were mild with a severe TEAE occurring in 1 patient (4.8%) (pulmonary hemorrhage identified after intubation).
- During Day 1 to study Day 4, following AeroFact dosing, there was 1 occurrence (10%) of moderate nasal congestion in Part I, and 5 occurrences (23.8%) of moderate nasal congestion and 1 occurrence (4.8%) of severe nasal congestion in Part II of the study. Nasal aspiration occurred in 2 patients (9.5%) in Part II on Day 1 in the study. Neither nasal congestion or nasal aspiration data were available from the historical control patients for comparison.
- One patient in Part I and 1 patient in Part II of the study had an SAE. Both patients had the SAE of culture-proven sepsis, which was not related to the study drug, the device, or the procedure, did not emerge during the treatment period, and resulted in death.
- Generally, the incidence of AEs associated with dosing tolerance in the first 24 hours was low; the incidence of AEs for AeroFact only vs. AeroFact plus bolus surfactant demonstrated comparability.
- The incidence of post-dose comorbidities of prematurity and AEs was low and consistent between the patients treated with AeroFact vs. historical controls.

2.2.3.2 APC-AF-CLN-001-Efficacy Analysis Conclusions:

- At 36 Weeks PMA, a larger proportion of patients receiving AeroFact in Part I and Part II of the study survived without BPD (88.9% and 78.9%, respectively) compared with Part I and Part II historical control patients (73.3% and 66.7%, respectively).
- The median (range) length of stay in the NICU for AeroFact patients in Part I and Part II was comparable to historical control patients.
- For AeroFact patients in Part I and Part II, the median time-to-failure using AeroFact criteria was consistently numerically greater than for historical control patients.
- For AeroFact patients in Part II, the median time-to-instilled surfactant was consistently numerically greater than for Part II historical control patients.
- No patients in the AeroFact group or in the historical control group required instilled surfactant after 72 hours of life.

- For patients receiving AeroFact treatment in Part II, the proportion of patients requiring rescue with instilled surfactant was lower than for the matched historical controls (25% vs 45%); this corresponded to a relative risk of 0.56, in favor of AeroFact treatment.

Study APC-AF-CLN-001 overall conclusions:

- Administration of AeroFact, up to 4 doses within 96 hours of life, was shown to be safe and well tolerated in patients ranging from 26 2/7 weeks to 30 4/7 weeks of gestational age and with weights between 640 to 1,664 grams.
- No AeroFact-treated patients in Part I or Part II of the study, or among the matched historical controls, received instilled surfactant beyond 72 hours of life.
- The need for rescue therapy by instilled bolus surfactant was lower in Part II of the study compared with matching historical controls; 5 AeroFact patients (25%) in Part II required rescue with surfactant bolus instillations vs. 27 patients (45%) who required instillations in the matching historical control group; this corresponded to a relative risk of 0.56, in favor of AeroFact treatment.

2.2.4 Summary of Pharmacokinetic Results

Pharmacokinetic studies are not applicable.

2.2.5 Summary of Known and Potential Risks of Aerosolized Surfactant Administration

Experimental use of inhaled surfactant is reported in the clinical literature and this use is expanding (Pillow and Minocchieri 2012, Minocchieri, Knoch et al. 2013, Minocchieri, Berry et al. 2018). Current publications indicate feasibility and safety of inhaled surfactant for managing preterm infants at risk for worsening RDS. SF-RI 1 was shown to have a significant effect on oxygenation, and none reported treatment-related AEs (Jorch, et al, 1997). As suggested, aerosolized surfactant is expected to augment current nCPAP therapy (Pillow and Minocchieri 2012, Soll, Edwards et al. 2013, Carlo 2014, Polin, Carlo et al. 2014) by delivering an effective surfactant dose, while minimizing the negative impacts of the current treatments for RDS.

The completed Phase 2a AeroFact™ study of inhaled SF-RI 1surfactant with nCPAP also showed no treatment-related AEs and appears safe and well tolerated.

2.2.6 Dosing Rationale for AeroFact

Marketed single doses of instilled Alveofact are 54 to 108 mg/kg. AeroFact dose selection was based on 50% delivery device efficiency from a nominal dose of 108 mg/kg and 216 mg/kg and additional approximetly 50% of the inhaled dose being delivered to lungs vs. the nasal passages. The maximal feasible dose determined in toxicology studies was 1,223 mg/kg/day.

This supports clinical dosing of up to a nominal dose of 864 mg/kg/day or 432 mg/kg/day (i.e. up to 4 doses in 96 hours after birth).

2.2.7 Risk Assessment

2.2.7.1 Risks to Subjects

The Sponsor has conducted risk analysis and the following clinical harms with overall high unmitigated risk have been identified:

- Hypoventilation, bradypnea, hypoxemia
- Progression of RDS (in the event of under-dosing)
- Skin irritation
- Pneumothorax, volutrauma

These clinical risks will be properly controlled and/or mitigated relative to the device design e.g. implementation of alarms, verification testing or labeling (instructions, warnings and cautions) prior to clinical trials on infants.

Furthermore, the drug delivery system will be tested for its safety following ISO and IEC standards for materials, biological and electrical safety, and electromagnetic compatibility.

The toxicology program in two species of newborn animals did not identify any risks with the dose or the route of administration.

The most common side effects reported when premature infants are given surfactant through the ETT or cannula are:

- decreases in oxygen saturation (SpO₂)
- plugging of breathing tube
- decreases in heart rate, reflux of surfactant into the breathing tube
- the need for extra mechanical breaths to be given from the breathing machine

These events are generally brief and not associated with serious complications or death.

Risks of aerosolized surfactant are unknown. However, due to the small aerosol size and gradual nature of the liquid aerosol administration, they are expected to be less than those associated with administration through an ETT/or cannula. The surfactant will be given by skilled caregivers in the NICU who can respond to all of these potential side effects should they occur. Risks of using the AeroFact drug delivery system are detailed in the Investigator's Brochure.

2.2.7.2 Benefits to Subjects

There is no guarantee that the infant will receive direct benefit from his/her participation in this study. Infants will have a 66% chance of receiving study drug. The benefits of being in this study may be the possibility that administering AeroFact may improve lung function and decrease the need for increases in respiratory support. Participation may provide information that may benefit other premature babies by helping to determine the safety and efficacy of aerosolized surfactant.

3 STUDY OBJECTIVES

3.1 Part I – Study Objective

3.1.1 Part I-Primary Objective

- To determine an optimal dose of AeroFact™ administered to preterm infants on nCPAP or nIMV vs. nCPAP or nIMV alone in reducing the incidence of intubation/cannulation and bolus surfactant instillation in the first 7 days after birth

3.1.2 Part I - Secondary Objectives

- To compare the time to the first intubation/cannulation across groups for infants requiring intubation due to surfactant deficiency
- To compare need for repeat surfactant dosing between groups within 7 days
- To evaluate the safety and tolerability of AeroFact administered by inhalation

3.2 Part II – Additional Objectives

- To evaluate pulmonary outcomes and respiratory resource utilization at 3, 6, 9, and 12 months corrected age.
- To evaluate respiratory morbidity per quarter and compare pulmonary morbidity across groups
- To evaluate early neurologic (modified GMFS) outcomes at 12 months corrected age

4 OVERALL STUDY DESIGN AND PLAN

The partially-blind, randomized, parallel-group, dose-ranging study is divided into 2 Parts. Part I includes birth through hospital discharge or 40 weeks PMA and Part II discharge through 12 months corrected age (Follow Up).

4.1 Part I

Part I is to determine the optimal dose of AeroFact compared to nCPAP or nIMV alone in reducing the incidence of intubation/cannulation and bolus surfactant instillation in the first 7 days after birth. 261 preterm infants who are at risk of worsening Respiratory Distress Syndrome (RDS), will be enrolled. The AeroFact dose and dosing strategy determined in this study will be used in a Phase 3 definitive trial. Preterm infants who require nCPAP (either by bubble CPAP or machine CPAP) or nIMV, and meet all inclusion and no exclusion criteria, will be enrolled into the study.

In the delivery room, infants will be stabilized on nCPAP/nIMV per site clinical guidelines. Once the infant has been stabilized, eligibility determined, and parental consent obtained, the infant will be block randomized in a 1:1:1 partially-blind fashion to receive one of two doses of AeroFact (Active) or Control. The randomization will be stratified by site and two gestational age groups (26 0/7 to 28 6/7 and 29 0/7 to 31 6/7 weeks). Patients who meet all inclusion, no exclusion criteria and are randomized to receive Active dose, will have the assigned treatment administered within first twenty-four hours after birth. Patients who are assigned to the Control group will continue to receive nCPAP/nIMV. If twins or triplets are enrolled, only the first sibling will be randomized

and subsequent siblings will receive the same treatment assignment. The Neonatal Intensive Care Unit (NICU) staff, the Principal Investigator (PI), the infant's family, and the sponsor will be blinded to AeroFact treatment allocation.

The study treatment allocation will be designated as either Active or Control. The Neonatal Intensive Care Unit (NICU) staff, the Principal Investigator (PI), the infant's family, and sponsor will be blinded to Active treatment dose allocation. Randomization will be a two-step process. Step 1: a designated member of the study staff will obtain a randomization envelope for the appropriate gestational age group, which will randomize the infant to either the Active or Control group. Step 2: active envelopes will be forwarded to the unblinded pharmacist or designee, where the active envelope will be opened and the Low or High dose group (108 mg/kg or 216 mg/kg) will be determined. Active drug dose will be calculated and dispensed according to the pharmacy manual instructions.

Active drug will be reconstituted according to the AeroFact package insert instructions or the pharmacy/respiratory therapy manual. Active study drug doses distributed by the pharmacy or designee will be labelled with patient ID. Parameters required to set up the AeroFact delivery system to administer the proper study treatment regimen (patient weight and mg/kg) will be programmed into the controller by the unblinded member of the study staff. For active drug doses, an unblinded study member will set up the AeroFact delivery system. The AeroFact system will be primed and set to deliver the appropriate dose. If the infant is randomized to Control, the infant will continue to receive nCPAP/nIMV.

While preparing the set-up for the AeroFact system, a privacy screen will be placed around the delivery system to ensure the blind is maintained. Once the system is set up, the privacy screen will be moved aside to allow access to the infant and controller. Prior to aerosol administration, infant will be transitioned from their standard CPAP/nIMV to the AeroFact interface. Administration of AeroFact will be managed by the unblinded staff member. When adjustment of the AeroFact system is required (drug vial change, alarms, etc.), a privacy screen should be utilized to mask the treatment allocation.

Oxygenation, ventilation parameters, and nasal congestion/aspiration will be monitored every 15 minutes for the duration of dosing or a minimum of two hours after the start of dosing by a blinded study or staff member. Dosing tolerance will be evaluated at 4 and 24 hours after the start of each AeroFact dose. AeroFact aerosol delivery will be stopped at the time of dose completion, but AeroFact tubing/nebulizer and vial will remain in place for a minimum of 2 hours. The AeroFact delivery system will be removed from the patient's bedside after dosing is completed or 2 hours have elapsed (whichever is longer) and patient may be transitioned back to their standard nCPAP circuit. A new drug delivery circuit must be used for each subsequent dose administered.

Infants receiving active drug will continue on nCPAP/nIMV after dose completion. If oxygenation and ventilation requirements increase within 96 hours after birth, AeroFact administration may be repeated up to three times for a total of 4 doses over the first 96 hours after birth. Re-dosing of AeroFact (same randomized group) will be allowed if the RSS to maintain SpO₂ between 90 and 95% is 1.5 to 2.39 and at least two hours have elapsed since the start of the previous dose:

- If FiO₂ > 0.23, re-dosing will occur.
- If FiO₂ ≤ 0.23, re-dosing is at the discretion of the investigator.

SpO₂ between 90-95% must be used to meet study eligibility through 96 hours for all study groups (Active/Control). Site-specific SpO₂ clinical guidelines may be used after 96 hours. Each site must use these guidelines uniformly across treatment groups. All infants randomized will be clinically managed until the criteria for treatment escalation have been met. If at any time the criteria for treatment escalation are met in any of the three treatment arms, intubation and/or bolus instillation of surfactant may be administered per site's standard of care. Oxygenation, ventilation parameters, nasal congestion/aspiration and dosing tolerance will be collected for each bolus instillation of surfactant.

Criteria for treatment escalation for AeroFact or nCPAP/nIMV only therapy includes any of the following:

1. Respiratory Symptom Severity (RSS) ≥ 2.4
2. Partial Pressure of Carbon Dioxide (PCO₂) > 65 mg Hg and/or pH < 7.20
3. Base deficit > 10 mEq/L, on two blood gases 4 hours apart
4. nCPAP > 8 cm
5. Three severe apneas with bradycardia within six hours requiring escalation of support
6. Infant's work of breathing has increased warranting escalating therapy, but infant does not meet RSS or other criteria above.

Data on all enrolled infants will be assessed through 40 weeks PMA or discharge from the NICU. Information to include: maternal/infant delivery, resuscitation history, oxygenation/ventilation parameters, concomitant medications of interest, and safety. Oxygenation and ventilation mode/parameters routinely monitored q 8 hours through Day 7, daily days 8 through 28, and daily at weeks 35 to 37 and 39 to 40 PMA/discharge. If an infant is discharged from the NICU prior to 36 and/or 40 weeks, a study member will call the family to verify the respiratory support status.

Co-morbidities of prematurity (e.g.: pneumothorax, IVH, PDA, NEC, sepsis, etc.) and adverse events (treatment-related or otherwise) will be collected to 40 weeks PMA/Discharge.

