2 BACKGROUND AND RATIONALE

2.1 Introduction

Aerogen Pharma is developing AeroFact, an investigational drug/device combination product consisting of lyophilized bovine-origin surfactant SF-RI 1 (sold in Europe since 1989 under the proprietary name AlveoFact®) administered following reconstitution to a 45 mg/ml suspension with semi-isotonic saline buffer using a proprietary breath-actuated vibrating mesh nebulizer with a nasal cannula interface.

Current surfactants used for prevention or treatment of Respiratory Distress Syndrome (RDS) in preterm infants are approved for delivery only as a liquid bolus instillation via an endotracheal tube (ETT) while intubated/cannulated. Intubation and cannulation with a tube into the trachea for surfactant administration are associated with adverse events (AEs) [1,2,3]. Access to surfactant therapy without invasive procedures that further exacerbate the condition is therefore a major unmet medical need in this vulnerable population. Reports suggest that AEs caused by intubation or cannulation can be avoided if there is a means of non-invasive delivery, i.e. aerosolized surfactant delivered through nasal continuous positive airway pressure (nCPAP) [5].

Current therapies for RDS in preterm infants are associated with the following challenges:

- Endotracheal intubation of preterm infants is an invasive procedure associated with airway tissue trauma, vagal stimulation, hypoxia, and bradycardia [1,2,3]. Additionally, insertion of small catheters into the infant trachea and positioning above the bifurcation can be traumatic. Both techniques require specialized skills, medical support, and training that must be kept current via frequent practice.
- Liquid bolus surfactant instillation via ETT is associated with airway obstruction (due to the large volume of liquid relative to preterm infant lung volumes) and transient physiological events such as hypoventilation, hyperventilation, changes in systemic blood pressure, alterations of cerebral blood flow, and other pulmonary and neurological effects.
- Respiratory support with nCPAP alone, albeit less traumatic compared to intubation/mechanical ventilation, results in delayed delivery of surfactant or absence of exogenous surfactant administration. This can lead to:
 - Atelectasis
 - Stress within the lungs associated with pneumothoraces and bronchopulmonary dysplasia (BPD)

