4.4 Treatment

4.4.1 Part I

In the two active arms of this study, nominal doses of 108 mg/kg or 216 mg/kg aerosolized SF-RI 1 will be administered by a dedicated drug delivery system to infants who are receiving nCPAP/nIMV. A maximum of four doses over 96 hours will be permitted. Re-dosing will be allowed if the RSS to maintain SpO₂ between 90% and 95% is 1.5 to 2.39 and at least 2 hours have elapsed since the start of the previous dose:

- If FiO₂ > 0.23, re-dosing will occur.
- If FiO₂ ≤ 0.23, re-dosing is at the discretion of the investigator.

In the control arm, infants will receive nCPAP/nIMV alone as determined by their clinical team until criteria for escalation of treatment occurs. SpO₂ between 90-95% must be used to meet study eligibility through 96 hours for all study groups (Active/Control). Site-specific SpO₂ clinical guidelines may be used after 96 hours. Each site must use these guidelines uniformly across treatment groups.

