6.4 Study Medication Supply, Preparation, and Administration

6.4.1 Study Medication Supply

The pharmaceutical dosage form of AeroFact is lyophilized SF-RI 1 dry powder in a type 1 glass vial (nominal volume 5 mL). The labelled vial size is 108 mg. The closure is a gray butyl rubber, fluoropolymer-coated, 13 mm stopper with an aluminum/propylene, blue, 13 mm flip-off seal. The current manufacturing facility is BAG Health Care (BAG) GmbH, [name].

The pre-filled syringe is hydrolytic glass type 1, 3.0 mL. It is aseptically filled to 2.4 mL with 0.45% (semi-isotonic) saline buffer for reconstituting the 108 mg vials. There are two variants. The first, manufactured by IDT Biologika, Dessau-Rosslau, Germany, is a luer-slip format with a chlorobutyl rubber (4432/50) gray plunger stopper and a synthetic gray polyisoprene tip cap (7028/55). The second, manufactured by S.C. Rompharm Company S.R.L, Ilfov County, Romania, is a luer-lock format with a gray bromobutyl rubber (FM 257/2) plunger stopper, and a synthetic gray isoprene-bromobutyl blend tip cap (7025/65).

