6.5.4 Device Replacement

One device (controller, drug delivery circuit and associated components) is expected to perform throughout the duration of dose. If the controller or the drug delivery circuit are not functioning optimally for any reason, instructions for trouble-shooting provided in the device instruction manual should be followed by the trained unblinded staff. If one or more devices need to be

replaced, the reason should be documented in the patient's medical record and appropriate study records. Additional devices are provided for this purpose. The unique serial numbers of the new controller and drug delivery circuit will be recorded in the patient's medical record and study records.

Controllers and drug delivery circuits should be replaced at any time if there is a confirmed or suspected malfunction.

- Device substitution, whether controller or circuit, should be recorded on the appropriate page of the study records.
- Notation must be made if the investigator suspects the device is not performing optimally for any reason.

If the Device fails, there is no way to restart a partial dose.

- For any partial dose delivered, note the amount of dose remaining on the controller drug delivery screen (if available) and record on Unblinded dosing record. Otherwise estimate the amount delivered and record on Unblinded dosing record. This will count as one of the 4 delivered doses. Patient will be eligible for repeat dosing 2 hours after the start of the previous dose.
- Only a maximum of four doses of AeroFact will be delivered.

For device performance problems or complaints, the Sponsor or the Sponsor's designee should be contacted within 48 hours. Complaints should be submitted to: [contact]. Failed devices and drug delivery circuits will be inventoried and returned to the Sponsor or the Sponsor's designee.

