6.6 Blinding

Clinical and research staff will remain blinded to dose level being administered with the exception of pharmacy staff or designee and respiratory therapy staff or designee. AeroFact drug delivery circuit will remain in line for the duration of dosing or a minimum of 2 hours, regardless of dose volume being administered.

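### The measures described do not secure the dose blind: the controller display is left unshielded during dosing, and the number of screened vial changes differs between 108 and 216 mg/kg

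*Combined protocol and SAP*

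**What the plan says.** Sections 6.6 and 12.6 promise that clinical and research staff stay blinded to dose level; Section 6.6 excepts pharmacy and respiratory therapy staff or their designees. Active versus Control is open: Section 10.1.3.1 has study staff learn when an infant is a control. Dose level is therefore the only blind.

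Section 4.1 sets out how it is kept. An unblinded person programs weight and mg/kg into the controller, primes the system behind a privacy screen and manages the dosing. After that, "Once the system is set up, the privacy screen will be moved aside to allow access to the infant and controller". The screen returns for interventions: "When adjustment of the AeroFact system is required (drug vial change, alarms, etc.), a privacy screen should be utilized to mask the treatment allocation". A blinded person records oxygenation, ventilation and nasal congestion every 15 minutes for at least two hours.

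Section 6.5.2.1 describes a touch-screen on which delivery is set and monitored. Section 6.5.4, on device failure, tells staff to "note the amount of dose remaining on the controller drug delivery screen", qualified as applying where that figure is available, and to enter it on the unblinded record. Section 6.5.2.2 makes the drug vial the device's reservoir, and Section 6.4.1 gives its content: "The labelled vial size is 108 mg". Section 6.6 adds one further measure: "AeroFact drug delivery circuit will remain in line for the duration of dosing or a minimum of 2 hours, regardless of dose volume being administered".

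The text does not say what the display shows in normal dosing, does not require it to be turned away from blinded staff, and describes no dummy vial change.

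**The concern.** Two routes to the dose stay open if the plan is followed as written. First, a controller that holds the mg/kg setting, and may show dose remaining, stands unscreened near someone who is meant not to know the dose. Second, the higher dose needs more vials. Each change brings the screen back, and infant weight is recorded at screening (Section 10.1.2). The screen conceals what the operator does, not the fact that an episode occurred.

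At stake is the choice of dose. The primary objective (Section 3.1.1) is an optimal dose, and Section 4.1 carries that dose into Phase 3. Several inputs to the 216 versus 108 mg/kg comparison rest on judgement: escalation for work of breathing when no other criterion is met, re-dosing at FiO2 of 0.23 or less (both Section 4.1), and the none-to-severe congestion grade (Section 10.1.4.1), which the blinded observer assigns. Expectation about dose can enter through each of these.

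**Working it through.** **Inputs.** Section 4.4.1: "nominal doses of 108 mg/kg or 216 mg/kg aerosolized SF-RI 1 will be administered". Vial content is 108 mg (Section 6.4.1). Diluent, same section: "It is aseptically filled to 2.4 mL with 0.45% (semi-isotonic) saline buffer for reconstituting the 108 mg vials". Concentration, Section 2.1: "administered following reconstitution to a 45 mg/ml suspension". Weight is below 2.0 kg (Section 5.1), with no lower limit in grams. Phase 2a weights were 640 to 1,664 g (Section 2.2.3.2).

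**The plan's own figure.** 108 mg / 2.4 mL = 45 mg/mL, as stated.

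**Vial changes per dose.** With weight w in kg, vials = ceil(108w/108) = ceil(w) at 108 mg/kg and ceil(216w/108) = ceil(2w) at 216 mg/kg. Changes = vials − 1.

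| Weight | 108 mg/kg | 216 mg/kg |
|---|---|---|
| >0.5 to 1.0 kg | 0 | 1 |
| >1.0 to 1.5 kg | 1 | 2 |
| >1.5 to <2.0 kg | 1 | 3 |

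Evaluated gram by gram, the counts differ at every weight from 501 to 1999 g (1,499 values), so throughout the Phase 2a range. They coincide only at 500 g or less.

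**Sensitivity to vial handling.** The documents give no priming loss, residue, overfill or rounding rule; these values are assumptions.

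| Assumption | Equal counts at | Share of 501–1999 g |
|---|---|---|
| Priming loss 0.05 vial | 951–975 g | 25/1,499 = 2% |
| Priming loss 0.2 vial | 801–900 g | 100/1,499 = 7% |
| Priming loss 0.4 vial | 601–800 g | 200/1,499 = 13% |
| Residue 5–20% per vial | none | 0% |
| Overfill 10% | 501–550 g | 50/1,499 = 3% |
| Rounding to whole vials | 501–749 g | 249/1,499 = 17% |

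These are shares of the weight range, not of infants; the documents give no weight distribution.

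**From vial changes to screen episodes.** Blinded staff see episodes, and alarms also cause them. Assume the two doses equally likely, weight known, the reason for each episode unknown, and alarm episodes Poisson with mean m per dose. Best-guess accuracy is ½ × Σ max(P_low, P_high). If the doses differ by k changes, this equals ½ × (1 + sum of the k largest Poisson probabilities).

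| m | k = 1 (>0.5 to 1.5 kg) | k = 2 (>1.5 kg) |
|---|---|---|
| 0.25 | ½(1 + 0.779) = 89% | ½(1 + 0.779 + 0.195) = 99% |
| 0.5 | ½(1 + 0.607) = 80% | ½(1 + 0.607 + 0.303) = 96% |
| 1 | ½(1 + 0.368) = 68% | ½(1 + 0.368 + 0.368) = 87% |
| 2 | ½(1 + 0.271) = 64% | ½(1 + 0.271 + 0.271) = 77% |

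The alarm rates are assumed; the documents give none. Chance is 50%.

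**The case against.** A reader might infer that the blind is broken outright, with blinded staff reading the dose off the controller. The documents do not support that. The operator is unblinded, the touch-screen serves its user, no section says that blinded staff look at it or that mg/kg stays on show, and the dose-remaining figure is conditional and belongs to device-failure handling. What stands is narrower: access is left open and no shielding is required.

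A reader might also infer that counting screen episodes reveals the dose at almost every weight. That would need the reason for each episode to be known. Alarms share the same screen, and Section 4.1 says the system is primed, so equal counts at some weights are possible. One bedside change per vial is itself an inference, though the vial's role as reservoir and the mention of vial changes in Section 4.1 support it.

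A third tempting argument is that the higher dose runs longer or sounds different. No output rate or dose-specific duration is given, only about two hours per dosing. Aerosol is generated in step with the infant's breathing, nothing is said about noise, and the in-line rule already addresses duration. That argument is not made here.

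On consequence, both primary tests in Section 12.11 compare a dose with an already open control, and no formal test of 216 against 108 mg/kg is listed, so the stated error rate is untouched. Five of the six escalation criteria are measured or counted, and re-dosing is required above FiO2 0.23 when RSS is in range. These facts limit the room for bias but leave the discretionary inputs. Respiratory therapy staff know the dose by design, and the change proposed here does not alter that.

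Finally, the directions for use, the procedures manual and the pharmacy/respiratory therapy manual are not among the documents and may already contain safeguards.

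**Conclusion.** The concern holds in this form: the measures written into the protocol do not secure the trial's only blind. The vial arithmetic is firm, subject to one bedside change per vial; assumed priming, overfill or rounding equalises the counts over about 2–17% of the 501–1999 g range. The step from vial changes to a correct guess depends on an unknown alarm rate: about 64–89% at >0.5 to 1.5 kg and 77–99% above 1.5 kg, from one dose. Display exposure is a gap in the procedure, not an established disclosure.

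A reader might infer that the primary tests are compromised; the documents do not support this. The risk is expectation bias in the comparison used to choose between doses, and neither its direction nor its size can be derived from the documents. The change should be made; confidence is moderate.

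**What to change.** In Sections 4.1, 6.6 and 12.6:

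- **Display.** For the whole dosing period, keep the controller display facing only the unblinded operator. Turn or side-shield it; do not cover it, so that the operator still sees visual alarms.
- **Screen episodes.** In both dose arms, have the operator raise the screen the number of times that 216 mg/kg needs at that weight. At 108 mg/kg the shortfall is made up by sham episodes that involve the screen only and do not interrupt delivery. From the table of vial changes, this is one sham episode up to 1.5 kg (1 − 0 or 2 − 1) and two above that (3 − 1).
- **Optional check.** The blinded assessor records a dose guess after the first dose, and agreement is reported by arm.

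The cost is one or two sham screen episodes per low-dose administration and a means of turning or side-shielding the display, plus one CRF item if the guess is collected. The unblinded operator is already present, and no procedure is added for the infant. If the manuals already require these steps, the protocol sections should say so.
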